2.4.2 Prior, concomitant and post therapies

Prior, concomitant and post therapies entered into the database will be coded using the WHO Drug Reference List to allow for categorization by preferred term. In addition to categorizing therapies data by preferred term, drugs are classified according to their ATC classification in order to present how they are being utilized. The ATC classification allows for a summary of medications by a high-level common drug class.

Concomitant medications and significant non-drug therapies/procedures taken concurrently with the study drug everolimus will be listed and summarized by ATC class and preferred term by means of frequency counts and percentages.

These summaries and listings will include medications starting on or after the start date of everolimus, or medications starting prior to the start date of everolimus and continuing after the start date of everolimus. Medications starting more than 30 days after the last day of everolimus will not be included. Any prior concomitant medications or significant non-drug therapies/procedures starting and ending prior to the start of everolimus will be listed.

Systemic anti-angiomyolipoma medication since discontinuation of study treatment will be listed and summarized by ATC class and preferred term by means of frequency counts and percentages.

The Safety Set will be used for all the above-mentioned tables and listings.

2.5 Analysis of the primary objective

The primary objective in this study is to evaluate the safety of Afinitor® in Chinese adults with TSC-renal AML not requiring immediate surgery. For further details on safety analysis, please see safety analyses in [section 2.8](#).

2.5.1 Primary endpoint

The primary endpoints are incidence of adverse events and laboratory abnormalities. For further details, please see safety analyses in [section 2.8](#).

2.5.2 Statistical hypothesis, model, and method of analysis

Not applicable

2.5.3 Handling of missing values/censoring/discontinuations

Not applicable

2.5.4 Supportive analyses

Additional sensitivity analyses might be further conducted if needed to assess the impact of missing assessments and/or evaluate the effect of baseline demographic and disease characteristics of potential prognostic value on study objectives.

Additional sensitivity analysis can be done to assess the impact of COVID19.

2.6 Analysis of the key secondary objective

There is no key secondary objective.

2.7 Analysis of secondary efficacy objective(s)

The secondary objectives in this study are to evaluate the efficacy of Afinitor® in Chinese adults with TSC-renal AML not requiring immediate surgery with respect to angiomyolipoma response rate, angiomyolipoma progression, and renal function change from baseline.

2.7.1 Secondary endpoints

The efficacy endpoints will be based on the independent central radiology review of CT/MRI assessments of the kidneys to determine the volumes of target lesions in the kidneys.

The efficacy analysis will be performed using the FAS.

Definition

Each post baseline CT/MRI assessment of the kidneys will be classified by the Independent Central Radiology Review as either angiomyolipoma response, stable disease, angiomyolipoma progression or not evaluable, based on the combined radiological assessments of target angiomyolipoma volume, kidney volumes and new angiomyolipoma lesions.

An overall angiomyolipoma response will then be calculated by Novartis combining the angiomyolipoma radiological assessment as provided by the Independent Central Radiology Review and angiomyolipoma-related bleeding reported by the investigator on the Adverse

Events CRF page. Clinical review is required in order to identify all occurrences of angiomyolipoma-related bleeding reported by the investigators.

Angiomyolipoma response is defined as:

- A reduction in angiomyolipoma volume of at least 50% relative to screening, where angiomyolipoma volume is the sum of the volumes of all target angiomyolipomata identified at screening.

In addition, angiomyolipoma response requires satisfying all of the following criteria:

- No new angiomyolipomata ≥ 1.0 cm in longest diameter are identified
- Neither kidney increases in volume by more than 20% from nadir (where nadir is the lowest kidney volume obtained for the patient, separately for each kidney, previously in the trial including baseline)
- The patient does not have any angiomyolipoma-related bleeding of grade ≥ 2 (as defined by NCI Common Terminology Criteria for Adverse Events (CTCAE), version 4.03).

Angiomyolipoma progression is defined as one or more of the following:

- An increase from nadir of 25% or more in angiomyolipoma volume to a value greater than screening, where angiomyolipoma volume is the sum of the volumes of all target angiomyolipomata identified at baseline and where nadir is the lowest angiomyolipoma volume achieved by the patient previously in the trial (including screening)
- The appearance of a new angiomyolipoma ≥ 1.0 cm in longest diameter
- An increase from nadir of 20% or more in the volume of either kidney to a value greater than screening, where nadir is the lowest kidney volume obtained for the patient, separately for each kidney, previously in the trial (including screening)
- Angiomyolipoma-related bleeding grade ≥ 2 as defined by NCI CTCAE, version 4.03.

Stable disease (SD): insufficient shrinkage in angiomyolipoma volume to qualify for response and the absence of progression.

Not evaluable (NE): CT/MRI performed but not readable (e.g., not all designated target lesions are included in a follow up image due to technical error).

The **best overall angiomyolipoma response** is the best response recorded from treatment until the first to occur out of (i) angiomyolipoma progression, (ii) the cut-off date for the final analysis, (iii) the date when a further systemic anti-angiomyolipoma medication is started, (iv) the date of an angiomyolipoma-related surgery, or (v) the date of death.

Angiomyolipoma response rate

Angiomyolipoma response rate, is defined as the proportion of patients with best overall angiomyolipoma response status of “angiomyolipoma response” (as defined as above) during maximum treatment duration of 48 weeks using data from the Independent Central Radiology Review of CT/MRIs and the Adverse Events CRF page (to identify angiomyolipoma-related bleeding of grade 2 or worse as defined by NCI CTCAE version 4.03). Angiomyolipoma response rate will be calculated based on the FAS and presented together with an exact 95% confidence interval for all patients.

Overall angiomyolipoma response (either angiomyolipoma response, stable disease, angiomyolipoma progression or not evaluable) at each assessment will be summarised by frequency and percentage.

Supportive analyses will include descriptive summaries of the sum of the volumes of target angiomyolipoma lesions from both kidneys (mean, standard deviation, 25th and 75th percentiles, median, minimum and maximum) at each assessment, using the time windows defined in [Section 2.1.1.7](#). Change from baseline (actual and percentage) in the sum of volumes of target angiomyolipoma lesions will also both be summarized descriptively at each assessment.

A waterfall plot will present the best percentage change from baseline in target angiomyolipoma volume at each assessment.

Note that patients with best overall angiomyolipoma response of Not Evaluable will be treated as non-responders in the calculation of the best overall angiomyolipoma response rate in the FAS, but will be excluded from the denominator for the waterfall plots.

Angiomyolipoma progression

Angiomyolipoma progression, is defined as the proportion of patients with an angiomyolipoma progression during maximum treatment duration of 48 weeks, as defined as above, using data from the Independent Central Radiology Review of CT/MRIs and the Adverse Events CRF page (to identify angiomyolipoma-related bleeding of grade 2 or worse as defined by NCI CTCAE version 4.03).

Angiomyolipoma progression rate will be calculated based on the FAS and presented together with an exact 95% confidence interval for all patients.

Time to angiomyolipoma progression

Time to angiomyolipoma progression (TTAP) is defined as the time from the start date of everolimus to the date of the first documented angiomyolipoma progression, where angiomyolipoma progression is defined as above. TTAP will be censored if angiomyolipoma progression is not observed before the first to occur out of

- (i) the cut-off date for the analysis, or
- (ii) the date when a further systemic anti-angiomyolipoma medication is started, or
- (iii) the date of a angiomyolipoma-related surgery or
- (iv) the date of death.

The censoring date will be the date of the last adequate CT/MRI assessment occurring before the first of any of these four events to have occurred, or treatment day 1 if there were no adequate CT/MRI assessments performed post-baseline.

TTAP will be presented in months and is calculated as:

$$(\text{Date of angiomyolipoma progression/censoring} - \text{Start date of everolimus} + 1) \times 12 \div 365.25.$$

The TTAP distribution will be presented descriptively in the FAS using a Kaplan-Meier curve. Summary statistics from the Kaplan-Meier distribution will be determined, including the

median TTAP and the proportions of patients remaining progression-free at 3, 6, and 12 months. These statistics will be given as point estimates with 95% confidence intervals.

Per protocol, tumor assessment was done at Week 4, 12, 24 and 48. At database lock, it was observed that most patients were censored at treatment completion at the time of their Week 48 assessment, and only 3 out of the 40 patients had angiomyolipoma progression observed. 9 patients were discovered to have TTAP greater than the maximum treatment duration of 48 weeks + 7 day window, among which one patient had progressed; this patient had the longest TTAP in the analysis set.

Kaplan-Meier estimates up to 48 weeks can be interpreted as fully valid. However, beyond that point where censoring was occurring due to treatment completion, the estimates are extremely undependable due to the high variability introduced by the small number of patients remaining in the risk set. In particular, the progression event in the patient with the longest TTAP causes the KM curve to drop to zero which is not meaningful; it is just an artifact of the KM calculation. In order to perform a somewhat interpretable analysis at this late timepoint, a revised analysis was introduced in which all patient outcomes (censoring or event) occurring after the maximum treatment duration will be considered to have occurred at the same timepoint. Specifically:

For TTAP exceeding the maximum treatment duration of 48 weeks + 7day window (11.268 months), the TTAP will be reassigned to 11.268 months. Then the Kaplan-Meier curve will be re-computed using this revised time definition.

It should be kept in mind that the KM event rate at the end of the study using this approach is very likely still over-estimated: the KM curve still drops noticeably because there were only 9 patients in the risk set beyond the end of treatment. Nevertheless, there was no signal in the data of a likely large increase in that narrow timeframe. Although this revised estimate ignores an event when it actually occurred, it does allow incorporation of that single late event in a more reasonable manner than using the raw data. Therefore, it is reasonable to say that the estimates up to the end of the Week 48 assessment window can be interpreted as fully valid.

Time to angiomyolipoma response

Time to angiomyolipoma response is defined as the time from the start date of everolimus until the date of the first documented angiomyolipoma response, where angiomyolipoma response is as defined as above. Time to angiomyolipoma response applies only to patients who achieve an angiomyolipoma response, i.e., patients in the analysis will have known times to angiomyolipoma response and there will be no censored times.

Time to angiomyolipoma response is calculated in months as

$$(\text{Date of first AML response} - \text{Start date of everolimus} + 1) \times 12 \div 365.25.$$

The median time to angiomyolipoma response will be presented along with a 95% confidence interval, and the proportions of angiomyolipoma responders who respond by 3, 6, and 12 months will be provided.

Duration of angiomyolipoma response

Duration of angiomyolipoma response is defined as the time from the date of the first documented angiomyolipoma response until the date of the first documented angiomyolipoma progression, where angiomyolipoma response and angiomyolipoma progression are as defined as above. Duration of angiomyolipoma response applies only to patients who achieve an angiomyolipoma response.

Duration of angiomyolipoma response will be censored if angiomyolipoma progression is not observed before the first to occur out of

- (i) the cut-off date for the analysis, or
- (ii) the date when a further systemic anti-angiomyolipoma medication is started, or
- (iii) the date of a angiomyolipoma-related surgery, or
- (iv) the date of death.

The censoring date will be the date of the most recent CT/MRI assessment before the first of any of these four events occurred.

Duration of angiomyolipoma response is calculated in months as

$$(\text{Date of angiomyolipoma progression/censoring} - \text{Date of first angiomyolipoma response} + 1) \times 12 \div 365.25.$$

A Kaplan-Meier curve will be constructed, and the median duration of angiomyolipoma response will be presented along with 95% confidence intervals. In addition, the Kaplan-Meier estimates with 95% confidence intervals will be presented at 3, 6, and 12 months.

Change from baseline in renal function

Renal function will be assessed using the calculated creatinine clearance (CrCl) from the Cockcroft-Gault formula ([Cockcroft et al 1976](#)).

The proportions of patients with severe renal impairment (defined as calculated CrCl < 30 mL/min). In addition, the proportion of patients with NCI CTCAE grade 3/4 serum creatinine will be determined.

For creatinine clearance, changes from baseline will be summarized descriptively (mean, standard deviation, 25th and 75th percentiles, median, minimum and maximum) at each assessment in FAS. The proportions of patients with severe renal impairment and NCI CTCAE grade 3/4 serum creatinine will be summarized by means of frequency counts and percentage at each assessment. Creatinine and CrCl values will be listed at patient level by visit from FAS.

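### The SAP declares the time-to-progression curve valid to the end of the Week 48 window, where its own post-lock rule places a step that it calls over-estimated

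*SAP*

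**What the plan says.** SAP 2.7.1 (Time to angiomyolipoma progression) reports what was seen at database lock. On censoring it says: "most patients were censored at treatment completion at the time of their Week 48 assessment". It counts 3 progressions among the 40 patients. Nine patients had a TTAP beyond 48 weeks plus the 7-day window. One of the nine had progressed, and that patient had the longest TTAP of all.

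The section then makes five statements in this order:

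- "Kaplan-Meier estimates up to 48 weeks can be interpreted as fully valid".
- Beyond that point, "the estimates are extremely undependable due to the high variability introduced by the small number of patients remaining in the risk set".
- A revised rule is introduced: "For TTAP exceeding the maximum treatment duration of 48 weeks + 7day window (11.268 months), the TTAP will be reassigned to 11.268 months".
- With that rule, "the KM event rate at the end of the study using this approach is very likely still over-estimated", because there were "only 9 patients in the risk set beyond the end of treatment".
- In conclusion, "it is reasonable to say that the estimates up to the end of the Week 48 assessment window can be interpreted as fully valid".

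SAP 2.1.1.7 closes the Week 48 imaging window at study day 343, which is 48 weeks plus 7 days. SAP 2.7.1 and 2.7.2 plan Kaplan-Meier estimates at 3, 6 and 12 months.

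**The concern.** The reassignment time and the end of the Week 48 window are the same day. The concluding sentence therefore appears to cover the very step that the SAP has just called over-estimated. A report author who relies on that sentence could present the end-of-study TTAP estimate at face value, although one event among 9 patients drives it.

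The validity limit also moves within the passage, from 48 weeks to the end of the window. The reassignment cannot justify that move, because it changes nothing before 11.268 months.

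Finally, a 12-month estimate is planned for a curve on which nobody is followed for 12 months.

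**Working it through.** **Inputs**

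- 40 patients and 3 progressions; 9 patients beyond Week 48 + 7 days, of whom 1 progressed and 8 were censored (SAP 2.7.1). The other 31 patients hold 2 events, whose dates are not given.
- Week 48 visits fall within 7 days either side of Day 336 (Protocol 7.1), that is Days 329 to 343.
- Months = days x 12 / 365.25 (SAP 2.7.1).
- Intervals use Greenwood's variance on the log-log scale for Kaplan-Meier estimates, and the exact binomial method for proportions (SAP 2.7.2).

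**The SAP's own figures.** 48 x 7 + 7 = 343 days, and 343 x 12 / 365.25 = 11.26899 months. The SAP's 11.268 is this value truncated; rounding would give 11.269. In the raw data the last event has one patient at risk, so the factor is 1 - 1/1 = 0 and the curve falls to zero, as the SAP says. On the same scale Day 336 is 11.04 months and Day 329 is 10.81 months.

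**Who is at risk at the step.** The rule changes only times above the cut-off. Patients censored at an on-time Week 48 scan before Day 343 keep their own dates and have already left the risk set. The late progression is therefore divided by the SAP's 9, a factor of 1 - 1/9 = 8/9.

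**Size of the step.** With the two other events at risk sets r1 and r2, the progression-free estimate at the end of the curve is

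S = (1 - 1/r1)(1 - 1/r2)(8/9).

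| Position of the two other events | r1, r2 | S before step | S after step | Event rate (95% CI) | Points from the late event |
|---|---|---|---|---|---|
| Before any censoring | 40, 39 | 0.950 | 0.844 | 15.6% (4.0-50.6%) | 0.950/9 = 10.6 |
| After all other censoring among the 31 (extreme) | 11, 10 | 0.818 | 0.727 | 27.3% (9.7-62.9%) | 0.818/9 = 9.1 |

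In the first case the lower limit for S drops from 0.81 to 0.49 at the step. The crude rate is 3/40 = 7.5% (exact 95% CI 1.6-20.4%).

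**Dependence on Day 343.** Because 11.26899 exceeds 11.268, a patient with a TTAP of exactly Day 343 is still at risk at the step, whether or not the rule moves that patient. If such patients exist outside the nine, the denominator grows. With the two other events first:

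- 10 at risk: 0.950 x 9/10 = 0.855, an event rate of 14.5%.
- 15 at risk: 0.950 x 14/15 = 0.887, an event rate of 11.3%.

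**The 48-week limit against the window limit.** The raw and revised curves are identical before 11.268 months. Estimates between Day 336 and Day 343 are thus the same numbers under both. The passage places them first beyond the valid range and later inside it.

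**The 12-month estimate.** Twelve months is 365.25 days. The longest possible time on the revised curve is about 11.27 months. A 12-month figure from it would only carry the step forward.

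**The case against.** The strongest reply is disclosure. The risk set of 9, the likely over-estimation, the visible drop and the fact that the late event is not shown when it occurred all stand just before the closing sentence. The SAP adds that the data gave no hint of a large rise in that short interval. Other safeguards exist: numbers at risk will be shown (SAP 2.1), the crude progression rate with an exact interval is planned (SAP 2.7.1), and progressions will be listed with narratives (Protocol 10.5.2). The revision also improves on a raw curve that falls to zero. All of this stands and keeps the point small. It does not make the closing sentence true of the step.

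A second reply is that the sentence stops just short of 11.268 months, or that 48 weeks is shorthand for the Week 48 assessment. Either is possible, but neither is stated, and the sentence is drawn as a conclusion from the argument for including the late event. The 7-day shift alone would be a weak complaint.

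A third reply concerns the 12-month estimate: the SAP does not say that the raw curve is dropped, and raw times may or may not reach a year. The point is therefore confined to the revised curve.

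A reader might also infer more than the documents support:

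- That the late event adds 9.1 to 10.6 points whatever the undisclosed dates are. The truncated cut-off defeats this: with 15 at risk the step is 0.950/15 = 6.3 points.
- That 27.3% is a likely value. It needs both other events to come after all the other censoring among the 31, and the SAP gives no dates.
- That the revised curve and the crude rate contradict each other. Their intervals overlap.
- That the SAP must pool all Week 48 outcomes in one risk set. Such pooling would be a second post-lock choice in the drug's favour, and with no early censoring it only returns the crude 7.5%.

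**Conclusion.** The concern holds as a minor one. On its natural reading, the closing sentence of the TTAP passage claims a validity that the SAP has just denied to the estimate at that time point. With the SAP's own risk set of 9, the end-of-curve event rate is 15.6% with the two other events first and at most 27.3%, roughly two to four times the crude 7.5% (15.6/7.5 = 2.1; 27.3/7.5 = 3.6).

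The 8/9 factor and these rates assume that no patient outside the nine has a TTAP of exactly Day 343. The level between the two rates depends on event dates that the SAP does not give.

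The consequence is limited to how one descriptive, untested curve is read. Relative to the crude rate, the error runs against the drug.

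**What to change.** 1. Reword the closing sentence of the TTAP passage in SAP 2.7.1 so that the validity claim covers only estimates before Week 48 censoring begins (about Day 329, 10.81 months) and expressly excludes the step at 11.268 months.
2. For the revised curve, do not report a 12-month estimate. Report the estimate just before Week 48 censoring begins, with the number at risk, and refer to the planned crude progression rate and its exact interval for the end-of-study figure.
3. State the cut-off as Day 343 instead of 11.268 months, so that truncation does not catch Day-343 patients.

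A curve that pools all Week 48 outcomes in one risk set is optional. If shown, it should stand beside the curve from the SAP rule and be labelled a post-lock sensitivity display.

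The cost is one reworded sentence, one replaced time point and one cut-off given in days. The SAP loses a 12-month figure that the revised data cannot support.

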2.7.2 Statistical hypothesis, model, and method of analysis

This study has a single treatment arm and there are no statistical tests planned for any of the response rates.

Response rates

Responses will be summarized in terms of percentage rates with exact 95% confidence intervals. An exact binomial confidence interval ([Clopper and Pearson, 1934](#)) will be used, implemented using SAS procedure FREQ with the EXACT statement for one-way tables.

Time-to-event analyses

This section presents the general methodology used to analyze time-to-event variables, e.g., TTAP, time to angiomyolipoma response and duration of response.

An estimate of the time-to-event function will be constructed using the Kaplan-Meier (product-limit) method as implemented in the procedure LIFETEST with the METHOD=KM option. The Kaplan-Meier curve will be displayed.

Median time-to-event will be obtained along with a 95% confidence interval calculated from the procedure LIFETEST using the method of (Brookmeyer and Crowley, 1982).

Kaplan-Meier estimates of the time-to-event function with 95% confidence intervals at 3, 6, and 12 months, where 1 month is defined as $(365.25/12)=30.4375$ days, will be presented. The confidence intervals will be constructed using Greenwood's formula (Collett, 1994) for the standard error of the Kaplan-Meier estimate. The log-log transformation of the survivor function (Kalbfleisch and Prentice, 1980) will be used in order to ensure that the confidence limits remain in the interval [0, 1]. The complementary log-log transformation is implemented in the LIFETEST procedure using the option CONFTYPE=LOGLOG.

